9.5 Outcomes

9.5.1 Primary Outcome

Temporal Summation (TS). The primary endpoint will be SCS-induced changes in temporal summation (TS). TS refers to an increased perception of pain in response to sequential stimuli of equal physical strength (Fig. 9.1A). It is a quantitative sensory testing (QST) model of neural plasticity and central hyper-excitability that is thought to reflect the progressive increase in neuronal firing of dorsal horn neurons in response to repetitive nociceptive C-fiber stimulation (i.e., windup).⁵⁸ In this assessment, we will use a handheld pointed skin probe to apply fixed-intensity stimuli of 256 mN or 512 mN. The weight of the pointed skin probe (i.e., 256 mN or 512 mN) will be selected based on the sensitivity of the patient's painful and control testing sites. In this paradigm, we will apply a single fixed intensity stimulus (256 mN or 512 mN) using a handheld pointed skin probe perpendicular to the subject's skin for approximately 0.5 seconds. Following a 5-second pause, we will apply a train of 10 identical stimuli (256 mN or 512 mN) with a frequency of 1 Hz within an area of 1 cm².

Immediately following the single stimulus and the train of 10 stimuli, we will ask the subjects to report the pain intensity of the stimulus using a 0-100 NRS. We will conduct this testing paradigm (a single stimulus followed by a train of 10 stimuli) three times with the same 256 mN or 512 mN stimulator, and each cycle will be separated by at least 10 seconds. We will calculate TS scores by subtracting the average pain rating of the single-stimulus trials from the average pain rating of the ten-stimuli trials. If the difference is a positive number, we will conclude that there was pain summation, where larger numbers will indicate increased pain summation or TS. If the difference is zero or a negative number, we will conclude that there was no pain summation or TS. The primary endpoint will be the continuous TS values calculated at the end of each seven-day treatment period. Furthermore, at 15- and 30-seconds following the last train of 10 stimuli, we will ask subjects to rate any residual pain sensation in the testing area using the 0-100 NRS.

[figure not shown]

Figure 9.1. Quantitative sensory testing (QST). (A) Temporal summation (TS), (B) Conditioned pain modulation (CPM), and (C) Vibrometry.

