Conditioned Pain Modulation (CPM). We will use CPM to test the effect of a noxious “conditioning” stimulus on a “test” stimulus to determine the efficiency of (supraspinal) descending pain inhibition (Fig. 9.1B). We will use pressure delivered by the algometer as the test stimulus, and a contralateral thumbnail pressure (using MAST) as the conditioning stimulus. We will determine pressure-pain thresholds before and after application of a conditioning stimulus. The conditioning stimulus is a 60-second continuous pressure to the contralateral thumbnail at the exact or similar pain intensity as the test stimulus. During the first 30-s, subjects will rate the intensity of the thumbnail pressure alone on a VAS or a 0-100 NRS. Parallel to the last 30-seconds of CPM conditioning while the subjects’ thumb is still in the MAST device, we will reapply the test stimulus and determine pressure-pain thresholds. We will conduct the CPM test separately on the pain site and the control site. We will evaluate CPM as the mean difference in pressure-pain thresholds before and after application of a conditioning stimulus. If the difference in pressure-pain threshold is found to be negative, the subject is considered to have achieved an inhibitory CPM response; if the difference in pressure-pain threshold is found to be zero or positive, it is concluded that the subject did not exhibit a CPM response.

Other important considerations. If the participant has been diagnosed with peripheral neuropathy in the upper extremity that could potentially interfere with the MAST results, we will skip the MAST and thumb-based CPM procedures. However, the participant will complete the other tests. If the participant has a missing, severely malformed, or injured thumb on which testing is to be performed, we will conduct MAST testing on the opposite thumb, provided it is not missing nor injured. For example, we would conduct both familiarization and testing on the dominant thumb if the non-dominant thumb was abnormal, or vice-versa. To permit sufficient tissue recovery, we will provide a rest interval of 5-10 minutes between the MAST familiarization

protocol and the MAST test, if we conduct testing on the same thumb. We will record the thumb on which familiarization and testing occurred. If both thumbs are missing and/or injured, we will skip the MAST and the thumb-based CPM tests. However, the participant will complete the other tests.

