We will validate the design and parameters of our patient-specific computer models with detailed clinical measurements in each patient. We will determine two stimulation thresholds that are standard measurements with clinical SCS programming⁸⁹:

Perception threshold (PT) = amplitude at which the participant first detects the stimulation, usually felt as a tingling sensation (i.e., paresthesia), related to

DC fiber activation

Discomfort threshold (DT) = amplitude at which the stimulation becomes uncomfortable due to motor effects or other discomfort, related to DR fiber activation

While we do not know the neuromodulatory effects of various forms of clinically effective SCS, such as burst and kilohertz-frequency SCS, it is well accepted that stimulation at PT and DT correspond to dorsal column and dorsal root fiber activation, respectively.⁷⁶ Therefore, in each participant, we will measure the PT and DT for tonic 50 Hz, burst, and 1 kHz SCS. At PT, we will also have each patient indicate the areas of stimulation-induced paresthesias by drawing on a human figure on a tablet.⁹⁰ These drawings will help ensure that the models predict the correct activation in the spinal cord somatotopy corresponding to the paresthetic regions. If necessary, we will adjust the model parameters (e.g., tissue conductivities) until the models predict the appropriate activations at PT and DT for 50 Hz, burst, and 1 kHz SCS.

Spinal circuit model. We will implement a circuit model of pain processing in the dorsal horn based on the gate-control theory of pain.¹⁷ This circuit model will include populations of inhibitory interneurons (I), excitatory interneurons (E), wide-dynamic range (i.e., neurons that respond to both nociceptive and non-nociceptive inputs) projection neurons (W), and a mid-brain neuronal population (T) (Fig. 9.6). It will also include inputs from three types of afferent fibers: large-diameter myelinated somatosensory $A\beta$, thinly myelinated nociceptive $A\delta$, and unmyelinated nociceptive C fibers.

[figure not shown]

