We will validate the output of our population firing-rate model in multiple steps. We will ensure that our model reproduces well-known phenomenon, such as central sensitization or “wind-up”. Wind-up is an increased excitability of the neurons in the spinal cord, particularly the wide-dynamic range projection neurons, due to repetitive stimulation of C fibers. Therefore, we will generate repetitive low-frequency (1 Hz) C-fiber inputs and compare the output of our *W* population to previous experimental data demonstrating wind-up.^{94,96,104–107} As described in Section 9.5.1, temporal summation (TS) of pain is the human analogue of wind-up, and so we will also match the output or degree of central sensitization to the experimental measurements of TS. In our primary outcome considering SCS-induced changes in TS, we will apply a repetitive 1 Hz stimulus and have the patient rate their pain as a function of time. In human subjects, each subsequent stimulus becomes more painful and is believed to represent wind-up

within the spinal cord. Therefore, we will be able to compare increases in the pain ratings from our participants (reflecting wind-up) to increases in the output of the W population in our model.

We will also validate that our circuit model reproduces descending inhibition. We will compare our model results to the experimental measurements performed in the CPM paradigm. During this CPM paradigm, a patient receives a conditioning stimulus and a painful test stimulus and rates the pain of this test stimulus (Fig. 9.1B). In human patients, the conditioning stimulus has the effect of reducing the pain levels of the test stimulus and is believed to represent descending pain inhibition.¹⁰⁸ Therefore, we will compare the reduced pain levels observed during CPM in each patient to the changes in W output in our model produced by increased inputs from the T population. We will represent the test stimulus as increased inputs from the all three afferent populations ($A\beta = 9$ spikes/s, $A\delta = 9$ spikes/s, $C = 2.5$ spikes/s).^{96,103} We will represent the conditioning stimulus by increasing the weighting parameter between the T and W populations that would produce increased inhibition of W .⁹²

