Because these mechanistic questions are difficult to answer experimentally, we will also perform exploratory analyses with patient-specific computational models that will include: 1) electric-field models to estimate the direct neural response to SCS, and 2) circuit models to estimate the effects of SCS on pain processing in the spinal cord. We hypothesize that patient-specific models capture the details necessary to quantitatively describe the neural response to SCS and to correlate model-based predictions with experimental measurements of pain modulation. Therefore, we will develop patient-specific electric-field models that account for sources of interpatient variability (e.g., anatomy, electrode locations, stimulation parameters) for the 25 participants. We will define finite element models from the patient-specific preoperative and postoperative medical imaging. To estimate the direct neural response to SCS, we will then place multi-compartment neuron models within the patient-specific spinal cord anatomy.

The basic hypothesis of this study is that the physiological effects of SCS can be correlated with modulation of specific fiber pathways that help regulate pain processing within the spinal cord. However, the specific analgesic mechanisms of clinically effective SCS remain unknown. Therefore, as a second component of our computational modeling approach, we will develop a population firing-rate circuit model of pain processing in the spinal cord. We will use the direct neural response to SCS estimated from the electric-field models as the inputs to our circuit model. We will determine what types of spinal cord modulation best correlate with experimental measurements of pain modulation during SCS.

Finally, due to our poor scientific understanding of how SCS works and the limited individualization of this therapy, we consider current clinical implementation of SCS to be suboptimal. Therefore, in this exploratory analysis, we will use our computational models to identify stimulation protocols (e.g., alternative waveform parameters) that may improve the desired physiological effects and corresponding pain relief.

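### Model calibration and model validation are not separated for the stimulation thresholds or for temporal summation, and two stated validation inputs are not collected

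*Combined protocol and SAP*

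**What the plan says.** **Field model (9.5.2, Patient-specific computer modeling).** The finite element models start from published conductivity values. The plan then states: "We will validate the design and parameters of our patient-specific computer models with detailed clinical measurements in each patient". The measurements meant are the two programming thresholds: in each participant, "we will measure the PT and DT for tonic 50 Hz, burst, and 1 kHz SCS". If the model does not reproduce them, "we will adjust the model parameters (e.g., tissue conductivities) until the models predict the appropriate activations at PT and DT", for all three waveforms. Paresthesia drawings at PT are a further check, with no agreement criterion.

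**Circuit model (9.5.2, Spinal circuit model).** Validation has several steps. Wind-up in the model is compared with published experiments. TS is described as the human analogue of wind-up, "so we will also match the output or degree of central sensitization to the experimental measurements of TS". For the TS step the plan says "we will apply a repetitive 1 Hz stimulus and have the patient rate their pain as a function of time". For CPM it describes the patient rating the pain of the test stimulus. The model, now called validated, is then used to study mechanisms of pain relief.

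**Use of the models (1.3 and 9.6).** "We will determine what types of spinal cord modulation best correlate with experimental measurements of pain modulation during SCS". The models are also to be used to look for alternative waveform parameters.

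**What is measured.** Section 9.5.1: "Immediately following the single stimulus and the train of 10 stimuli, we will ask the subjects to report the pain intensity". CPM in 9.5.2: "We will evaluate CPM as the mean difference in pressure-pain thresholds before and after application of a conditioning stimulus".

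**The concern.** A validation step should be able to fail. If a disagreement with PT or DT leads to new conductivities until the disagreement is gone, the final agreement shows that the model could be fitted. It does not show that the model predicts. The same holds where the circuit output is matched to TS. If that output is later correlated with the same TS values, the association was put there by the fitting.

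The plan relies on the label: mechanism claims and the search for new waveforms are both made with a model described as validated. A separate difficulty is that two of the validation steps refer to data that the testing procedures do not produce, so they cannot be carried out as written.

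**Working it through.** The documents give no agreement criterion, tolerance or sample size for the modelling, so there is no figure to reproduce. The check sets sections side by side, with some counting.

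**1. Thresholds.**
- Types per participant: 2 thresholds x 3 waveforms = 6.
- Types that may be used for adjustment: 6. Types reserved for validation: 6 - 6 = 0. No visit or participant is reserved either.
- If only the 50 Hz pair were used for calibration: 6 - 2 = 4 types held out per participant.
- Ceiling: 4 x 25 = 100, or 4 x 20 = 80 with the 20 completers assumed in 9.2. Both are upper limits, because participants without suitable preoperative imaging are not modelled (9.5.2), and those who become pregnant or decline the pregnancy test have no CT (7.4).

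**2. What fit after tuning is worth (illustration only).** The number of adjustable parameters is not stated, so k = 1 to 6 is assumed. Six targets were fitted by least squares to pure-noise predictors, with 4,000 simulations per k. The expected in-sample share explained is k/6.

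| k | Share of the 6 targets explained in-sample | Mean held-out correlation |
|---|---|---|
| 1 | 0.17 | 0.00 |
| 2 | 0.33 | -0.01 |
| 3 | 0.50 | -0.01 |
| 4 | 0.67 | 0.00 |
| 5 | 0.83 | 0.00 |
| 6 | 1.00 | 0.00 |

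A finite element model is more constrained than a linear fit to noise, so these are not estimates for this trial. They show only that fit after adjustment and prediction are different quantities.

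**3. Circuit model and TS.** The plan does not say which treatment period's TS is used for matching or which parameters are free. Nothing therefore prevents matching and testing on the same TS values. For CPM the plan says compare rather than match. However, the conditioning stimulus is represented by raising an inhibitory weight, so the direction of the effect is imposed.

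**4. Data assumed and data collected.**

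| Step in the circuit-model text | Assumed | Collected |
|---|---|---|
| TS | Pain rated over time in the 1 Hz train | 3 cycles, each with 1 rating after the single stimulus and 1 after the train: 3 + 3 ratings, 0 within the train. Residual pain at 15 s and 30 s after the last train |
| CPM | Rating of the test stimulus | Pressure-pain thresholds for the test stimulus. Only the thumbnail conditioning pressure is rated |

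**5. Which TS test is fair after fitting to Sham.** Let S be Sham TS and A, A1, A2 be active-period TS, with equal variances and common correlation r. Take r = 0.5, the value that 9.2 assumes between TS measurements in the same subject. Consider a model that merely reproduces S and knows nothing about the waveforms:
- Against the active level: corr(S, A) = r = 0.5.
- Against the change from Sham: corr(S, A - S) = -(1 - r)/sqrt(2(1 - r)) = -sqrt((1 - r)/2) = -sqrt(0.25) = -0.5.
- Against a difference between active waveforms: the covariance is proportional to r - r = 0, so the correlation is 0.

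Only the third comparison is free of a built-in association under these assumptions.

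**The case against.** The strongest reply is that much of the modelling is still testable, and this stands. A reader might infer that Aims 2 and 3 cannot test whether the models predict anything, or that no data are left for validation. The documents do not support that:
- PT and DT are programming thresholds, not pain outcomes. Correlating the field model with TS, CPM or VAS (Aim 2) remains a test outside the tuning data.
- The comparison of responders with non-responders, defined on VAS in 9.6, is not described as a tuning step. Nor are the comparison of effective with ineffective settings or the comparison of wind-up with published data.
- Adjustment to PT and DT is conditional and starts from published conductivities, so an untuned prediction will exist. The plan does not undertake to report it, and any disagreement still ends in adjustment.
- Section 6.2 lists PT, DT and paresthesia mapping at Visits 2 to 6, so repeat measurements may be available.
- Ratings after one and after ten stimuli are collected, so the rise in pain ratings can be compared with the rise in model output. Only the time course within the train is missing.

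The modelling is also labelled exploratory throughout. That limits the consequences, but it does not make a fitted quantity a validated one.

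**Conclusion.** The point holds in this form. For PT/DT, and for TS in the circuit model, the plan counts as validation the same measurements that the models may be adjusted or matched to. Agreement on them is not evidence of prediction, and a later correlation of the circuit model with the same TS values is circular. The circularity is confined to those values and does not extend to pain measures that were not used in fitting.

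In size, 0 of 6 threshold types are reserved for validation, where 4 of 6 could be. Two validation inputs (ratings within the train and ratings of the CPM test stimulus) are not collected. The count does not measure a bias. The actual effect depends on how many parameters are adjusted and on which TS data are matched, and the documents state neither. The primary TS analysis in 9.6 does not depend on the models and is unaffected.

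**What to change.** 1. **Field model.** Before any adjustment, report predicted against measured PT and DT with the published conductivities. Then calibrate on the 50 Hz PT and DT only, freeze the parameters, and report predicted against measured PT and DT for burst and 1 kHz as the validation. Call any later refit to all thresholds calibration.
2. **Circuit model.** Call the TS matching calibration. Fit to Sham-period TS only, freeze the model, and test it on active-period TS not used in fitting. Use contrasts that do not reuse the Sham value, such as differences between active waveforms, or leave-one-participant-out prediction. Burst against 1 kHz is the cleanest contrast, because 50 Hz is always given last and 6.2.3 acknowledges a possible order effect.
3. **Text.** Reword the circuit-model section to use the single- versus ten-stimuli contrast of 9.5.1 and the CPM shift in pressure-pain threshold. State how a threshold shift is expressed in model output, and keep the sign convention of the CPM section.

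The cost is wording, a fixed order of analysis and slightly more analysis. No new measurement is needed, since the thresholds and TS are already scheduled. The fit at the validation step will be less close, because fewer data are used for tuning.

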9.6 Data Analyses

Analysis of the primary efficacy endpoint(s): The primary endpoint will be SCS-induced changes in temporal summation (TS) (see Section 9.5.1). We will use a repeated-measures approach in which the continuous TS values will be calculated at the end of each seven-day treatment period, i.e., type of SCS. To analyze SCS-induced changes in TS measured at the end of each treatment period, we will use linear mixed-effects models that will include a participant-level random intercept to account for correlations of measurements from the same participant. We will obtain the least-squares estimates of the mean TS for the treatments and perform group comparisons with the appropriate contrasts. We will establish statistical significance with two-sided $p < 0.05$. We will utilize a per-protocol analysis dataset. We will only consider randomized participants who completed the Sham SCS treatment along with at least one other active (i.e., burst, tonic 1 kHz, tonic 50 Hz) SCS treatment along with the associated outcome measures for each treatment.

Analysis of the secondary endpoint(s): N/A.

Baseline descriptive statistics: We will use descriptive statistics to assess data quality and characterize relationships between variables. We will list the aggregate data using means and standard deviations for normally distributed data and medians and interquartile ranges for non-normal data. We will consider several baseline demographics and clinical characteristics, such as gender, pain duration, pain diagnosis, previous back surgery, and co-treatments (e.g., opioids, antidepressants, anticonvulsants, NSAIDs/simple analgesics, other). We will consider the QST outcome measures characterizing baseline static and dynamic pain processing. Finally, we will also consider the exploratory outcome measures related to baseline pain intensity, pain quality, pain spread, and quality of life.

Sub-group analyses: This study is an exploratory mechanistic study examining the physiological effects of multiple forms of SCS on sensory processing. Due to the small number of participants that will be considered in this study (i.e., $n=20$), we will not analyze primary or exploratory endpoints based on age, race/ethnicity, or other demographic characteristic(s). However, sex has been shown to be an important variable to consider in chronic pain and sensory processing. Therefore, although we may not detect significant differences due to the

small sample size in this exploratory study, we will consider sex as a biological variable when analyzing the primary and exploratory endpoints.

Tabulation of individual participant data: We will list individual participant data with regards to the primary outcome. For each type of SCS (Burst-SCS, 1kHz SCS, 50Hz SCS, Sham SCS), we will list the TS value calculated for each individual participant. We will use the mean TS value to quantify SCS-induced changes in TS. For the exploratory endpoints, we will list the aggregate data using means and standard deviations for normally distributed data and medians and interquartile ranges for non-normal data.

Exploratory analyses: To investigate the anti-nociceptive effects of SCS, we are proposing to conduct an exploratory, mechanistic, placebo-controlled study in 25 patients undergoing SCS for chronic pain. We will use quantitative sensory testing (QST) to assess spinal and supraspinal pain processing. In addition to the primary outcome described in Section 9.4.2, we will perform several exploratory analyses. We will evaluate the effects of somatosensory stimuli using static QST measures of sensory detection threshold, pain threshold, and/or tolerance to stimuli (i.e., vibratory threshold, pressure-pain threshold). We will also assess dynamic central pain-processing mechanisms, such as endogenous pain inhibition, by measuring pain sensitivity concurrent with the application of a conditioning stimulus (i.e., conditioned pain modulation (CPM)).¹⁵ Furthermore, we will obtain outcome measures to assess changes in pain intensity, pain quality, pain spread, and quality of life. Additional exploratory outcomes will include patient-reported VAS ratings for back, leg, and general pain,^{1,2} and several self-reported patient questionnaires, such as the Short-Form McGill Pain Questionnaire to assess quality of pain,³ Michigan Body Map to quantify the degree of widespread body pain,⁴ EQ-5D to characterize quality of life,⁵ Pain Disability Index (PDI) to measure pain-related disability,⁶⁸ and questionnaires from the Patient Reported Outcomes Measurements Information (PROMIS)⁶. We will identify responders as patients who demonstrate a $\geq 50\%$ reduction in average pain intensity (as measured by the VAS) with active SCS as compared to sham stimulation, a standard criterion for success with SCS.²² We hypothesize that patients who respond to specific types of SCS will show decreased spinal segmental sensitivity, particularly decreased vibration sensitivity and pressure-pain sensitivity. We believe that effective SCS will also modulate dynamic central pain-processing mechanisms. We hypothesize that effective types of SCS (i.e., patients who show $\geq 50\%$ reduction in average pain intensity) will reduce TS (primary outcome) and improve inhibitor CPM.

Because these mechanistic questions are difficult to answer experimentally, we will also perform exploratory analyses with patient-specific computational models that will include: 1) electric-field models to estimate the direct neural response to SCS, and 2) circuit models to estimate the effects of SCS on pain processing in the spinal cord. We hypothesize that patient-specific models capture the details necessary to quantitatively describe the neural response to SCS and to correlate model-based predictions with experimental measurements of pain modulation. Therefore, we will develop patient-specific electric-field models that account for sources of interpatient variability (e.g., anatomy, electrode locations, stimulation parameters) for the 25 participants. We will define finite element models from the patient-specific preoperative and postoperative medical imaging. To estimate the direct neural response to SCS, we will then place multi-compartment neuron models within the patient-specific spinal cord anatomy.

The basic hypothesis of this study is that the physiological effects of SCS can be correlated with modulation of specific fiber pathways that help regulate pain processing within the spinal cord. However, the specific analgesic mechanisms of clinically effective SCS remain unknown. Therefore, as a second component of our computational modeling approach, we will develop a population firing-rate circuit model of pain processing in the spinal cord. We will use the direct neural response to SCS estimated from the electric-field models as the inputs to our circuit model. We will determine what types of spinal cord modulation best correlate with experimental measurements of pain modulation during SCS.

Finally, due to our poor scientific understanding of how SCS works and the limited individualization of this therapy, we consider current clinical implementation of SCS to be suboptimal. Therefore, in this exploratory analysis, we will use our computational models to identify stimulation protocols (e.g., alternative waveform parameters) that may improve the desired physiological effects and corresponding pain relief.

